### **5.3.2 Caffeine, Alcohol, and Tobacco**

Caffeine, alcohol, and tobacco will be restricted as follows:

- During each period, participants must abstain from ingesting caffeine- or xanthine-containing products (e.g., coffee, tea, cola drinks, and chocolate) for 48 hours before the start of dosing until after collection of the final PK sample.

- Alcohol must not be consumed from 48 hours before screening, 48 hours before admission until completion of follow-up visit on Day 13 of Period 2.
- Participants who use tobacco products will be instructed that use of nicotine-containing products (including nicotine patches) will not be allowed from screening until after the final follow-up visit.

### **5.3.3 Activity**

Participants must abstain from strenuous exercise for at least 72 hours before each blood collection for clinical laboratory tests. Participants may participate in light recreational activities during study (e.g., watching television, reading).

## **5.4 SCREEN FAILURES**

Screen failures are defined as participants who consent to participate in the clinical study but are not subsequently enrolled to study treatment.

The Investigator will maintain a screening log to record details of all participants screened and to confirm eligibility or record reasons for screening failure.

If a participant fails an inclusion/exclusion criterion due to a transient and non-clinically significant condition at screening, the Investigator may repeat the relevant screening assessment(s) within the 28-day screening period. If the participant fails a second time they will be classed as a screen failure and cannot be re-screened.

Re-screening is allowed for participants who were screened in the study and met study inclusion/exclusion criteria but failed to be enrolled within 28 days after the start of screening period because the enrollment was suspended. In order to re-screen such a participant, all inclusion and exclusion criteria should be re-evaluated and all applicable screening assessments repeated if done more than 28 days prior to the enrollment.

## **5.5 RECRUITMENT PROCEDURES**

Participants will be identified for potential recruitment using, clinical database and IEC/IRB approved newspaper/radio/television/Social Network Service/campus poster advertisements, mailing lists and other distributable documents, prior to consenting to take place on this study.

## **6. TREATMENTS**

Study treatment is defined as any investigational treatment(s), marketed product(s), placebo, or medical device(s) intended to be administered to a study participant according to the study protocol.

The investigational medicinal products (IMPs) required for completion of this study will be RO7049389 and pitavastatin. RO7049389 will be supplied centrally by the Sponsor

and pitavastatin (LIVALO® manufactured by Kowa) will be sourced locally and reimbursed by the Sponsor.

All study drug administration will be at the study center under supervision of site staff.

## 6.1 TREATMENTS ADMINISTERED

[Table 4](#) summarizes the treatments administered.

**Table 4 Summary of Treatments Administered**

Study Treatment Name:	RO7049389	Pitavastatin
Dosage Formulation:	Tablet	Tablet
Unit Dose Strength(s):	200 mg	2 mg
Dose:	800 mg BID	2 mg
Route of Administration:	Oral	Oral
Dosing Instructions:	4 tablets to be taken, with food	1 tablet to be taken, with food
Packaging and Labeling:	Study treatment will be provided in labeled bottles.	
Manufacturer	F. Hoffmann-La Roche Ltd	Kowa

Study treatments will be administered orally to the participants by investigational staff for all dosing with still water at room temperature.

Pitavastatin will be administered orally to participants by investigational staff in the morning on Day 1 of Period 1 and Day 4 of Period 2. Thirty minutes before the administration, a standard meal will be served to participants, which should be consumed within thirty minutes. RO7049389 will be administered orally to participants by investigational staff from Day 1 to Day 6 of Period 2 twice daily. The first daily dosing will be administered in the morning and the second daily dose will be in the evening, with approximately 12 hours interval. In the morning of Day 4 of Period 2, pitavastatin will be administered together with RO7049389.

For RO7049389, please see the [RO7049389 Investigator's Brochure](#) for more details.

For pitavastatin, see the local prescribing information for more details.

## 6.2 PREPARATION/HANDLING/STORAGE/ACCOUNTABILITY

For RO7049389, study drug packaging will be overseen by the Roche clinical trial supplies department and bear a label with the identification required by local law, the protocol number, drug identification and dosage.

The packaging and labeling of the RO7049389 will be in accordance with Roche standard and local regulations.

The investigational site will acknowledge receipt of RO7049389 and confirm the shipment condition and content. Any damaged shipments will be replaced.

Upon arrival of the RO7049389 at the site, site personnel will complete the following:

- Check the IMPs for damage.
- Verify proper identity, quantity, integrity of seals and temperature conditions.
- Report any deviations or product complaints to the Monitor upon discovery.

The qualified individual responsible for dispensing the study treatment will prepare the correct dose.

The Investigator or delegate must confirm appropriate temperature conditions have been maintained during transit for all study treatment received and any discrepancies are reported and resolved before use of the study treatment.

Pitavastatin (LIVALO® manufactured by Kowa) will be sourced locally and reimbursed by the Sponsor.

Only participants enrolled in the study may receive study treatments and only authorized site staff may supply or administer study treatments. All study treatments must be stored in a secure, environmentally controlled, and monitored (manual or automated) area in accordance with the labeled storage conditions with access limited to the Investigator and authorized site staff. Film-coated tablets of RO7049389 should be stored under the recommended storage conditions “Store at 2-8°C, protect from light and moisture”.

The Investigator, Institution, or the Head of the Medical Institution (where applicable) is responsible for study treatment accountability, reconciliation, and record maintenance (i.e., receipt, reconciliation and final disposition records).

IMPs will either be disposed of at the study site according to the study site’s institutional standard operating procedure (SOP) or returned to the Sponsor with the appropriate documentation. The site’s method of IMP destruction must be agreed upon by the Sponsor. Local or institutional regulations may require immediate destruction of used IMP for safety reasons. The site must obtain written authorization from the Sponsor before any IMP is destroyed, and IMP destruction must be documented on the appropriate form.

## **6.3 MEASURES TO MINIMIZE BIAS: RANDOMIZATION AND BLINDING**

### **6.3.1 Method of Treatment Assignment**

This is a fixed sequence study. Randomization is not applicable.

### **6.3.2 Blinding**

This is an open-label study, blinding procedures are not applicable.

## **6.4 TREATMENT COMPLIANCE**

The qualified individual responsible for dispensing the study treatment will prepare the correct dose according to the instructions given in Section 6.1. This individual will record the date dispensed and participant number on the Drug Accountability Record.

## **6.5 CONCOMITANT THERAPY**

### **6.5.1 Permitted Therapy**

Any medication or vaccine (including OTC or prescription medicines, approved dietary and herbal supplements, nutritional supplements) used by a participant from 30 days prior to screening until the follow-up visit must be recorded along with reason for use, dates of administration (including start and end dates) and dosage information (including dose and frequency).

The Medical Monitor should be contacted if there are any questions regarding concomitant or prior therapy.

All concomitant medications should be reported to the Investigator and recorded on the Concomitant Medications electronic Case Report Form (eCRF).

All therapy and/or medication administered to manage adverse events should be recorded on the Adverse Event eCRF.

The following medications will be permitted:

- Medications used to treat AEs may only be prescribed after consultation with the Sponsor (with the exception of acetaminophen/paracetamol), unless there is a medical need to ensure the well-being of the participant that should not be delayed. All therapy and/or medication administered to manage adverse events should be recorded on the Adverse Event eCRF.
- Hormone replacement therapy (HRT): permitted if initiated at least 2 months prior to study start.
- Occasional use of acetaminophen (up to a maximum dose of 2g/day up to 48 hours prior to dosing, not to exceed 4g total during the week prior to dosing) will be permitted.

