## **CONCOMITANT MEDICATIONS**

### **Permitted Therapy**

Any medication or vaccine (including OTC or prescription medicines, approved dietary and herbal supplements, nutritional supplements) used by a participant from 30 days prior to screening until the follow-up visit must be recorded along with reason for use, dates of administration (including start and end dates) and dosage information (including dose and frequency).

The following medications will be permitted:

- Medications used to treat AEs may only be prescribed after consultation with the Sponsor (with the exception of acetaminophen/paracetamol), unless there is a medical need to ensure the well-being of the participant that should not be delayed. All therapy and/or medication administered to manage adverse events should be recorded on the Adverse Event eCRF.
- Hormone replacement therapy (HRT): permitted if initiated at least 2 months prior to study start.
- Occasional use of acetaminophen (up to a maximum dose of 2g/day up to 48 hours prior to dosing, not to exceed 4g total during the week prior to dosing) will be permitted.

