#### **4.1.1 Length of the Study**

The total duration of the study for each participant will be about 12 weeks divided as follows:

- Screening: Up to 28 days.
- Period 1:
  - In clinic period: Days -1 to 4.
  - Treatment period: Day 1
- Wash-out Period: Defined as from Period 1 Day 1 to Period 2 Day 1 and lasts at least 7 days but not more than 21 days
- Period 2:
  - In clinic period: Days -1 to 7
  - Treatment period: Days 1 to 6
- Safety follow-up:
  - Period 2 Day 13
  - Period 2 Day 34 (Telephone call)

The participant has the option to stay in clinic during the whole Period 1 and wash-out period if agreed by Sponsor and the Investigator.

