### **6.5.2            Prohibited Therapy**

All medications (prescription and OTC) taken within 30 days of study screening will be recorded on the appropriate eCRF.

As a general rule, no concomitant medication will be permitted within 14 days prior to the first dosing or within 5 half-lives of the medication prior to the first dosing (whichever is longer), until the follow-up visit, with the exception of the cases listed in Permitted Therapy (See Section 6.5.1). Exceptions may be made on a case-by-case basis following discussion and agreement between the Investigator and the Sponsor after, the rationale for exception is discussed and clearly documented.

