### **8.3.1 Time Period and Frequency for Collecting Adverse Event and Serious Adverse Event Information**

The method of recording, evaluating, and assessing causality of AEs and SAEs and the procedures for completing and transmitting SAE reports are provided in [Appendix 2](#).

Investigators will seek information on adverse events at each participant's contact. All adverse events, whether reported by the participant or noted by study personnel, will be recorded in the participant's medical record and on the Adverse Event eCRF as follows:

**After informed consent** has been obtained **but prior to initiation of study treatment**, only serious adverse events caused by a protocol-mandated intervention should be reported (e.g., serious adverse events related to invasive procedures such as biopsies). Any other adverse event should not be reported.

**After initiation of study treatment**, all adverse events, regardless of relationship to study treatment, will be reported until 28 days after the last dose of study treatment.

**Post-study adverse events and serious adverse events:** The Investigator is not required to actively monitor participants for adverse events after the end of the adverse event reporting period (28 days after the last dose of study treatment).

However, if the Investigator learns of any SAE (including a death) or other adverse events of concern that are believed to be related to prior treatment with study treatment, at any time after a participant has been discharged from the study, and the Investigator considers the event to be reasonably related to the study treatment or study participation, the Investigator must promptly notify the Sponsor. For the procedure of reporting, see [Appendix 2](#).

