#### **8.10.3 Assessments at Study Completion/Early Termination Visit**

Participants who complete the last dose administration or discontinue from the study early will be asked to return to the clinic 7 days after the last dose of study treatment for a follow-up visit and 28 days after the last dose of study treatment for a follow-up call. The follow-up visit and follow-up call will be reported as the study completion visit in eCRF

In case of early termination of a participant, a blood sample for PK assessment of RO7049389 and pitavastatin should be collected at the time of discontinuation. Please also see Section 1.3 for activities that are required to be performed in case of an early termination.

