### **3.2. ASSESSMENT OF CAUSALITY**

Investigators should use their knowledge of the participant, the circumstances surrounding the event, and an evaluation of any potential alternative causes to determine whether or not an adverse event is considered to be related to the study treatment, indicating "yes" or "no" accordingly. The following guidance should be taken into consideration:

- Temporal relationship of event onset to the initiation of study treatment.
- Course of the event, considering especially the effects of dose-reduction, discontinuation of study treatment, or reintroduction of study treatment.
- Known association of the event with the study treatment or with similar treatments.
- Known association of the event with the disease under study.
- Presence of risk factors in the participant or use of concomitant medications known to increase the occurrence of the event.
- Presence of non-treatment-related factors that are known to be associated with the occurrence of the event.

For participant receiving combination therapy, causality will be assessed individually for each protocol-mandated therapy.

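### General concomitant-medication recording is written to stop at the follow-up visit, 19 to 21 days before adverse event collection and causality assessment end

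*Combined protocol and SAP*

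**What the plan says.** **Recording of medication.** Section 6.5.1 covers any medication or vaccine "used by a participant from 30 days prior to screening until the follow-up visit must be recorded along with reason for use". The synopsis (Section 1.1, Permitted Therapy) gives the same end point: "used by a participant from 30 days prior to screening until the follow-up visit must be recorded". Section 6.5.1 separately sends all medication given to manage an adverse event to the Adverse Event eCRF, with no end date.

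**Restriction on medication.** Section 6.5.2 runs its general restriction "until the follow-up visit, with the exception of the cases listed in Permitted Therapy", so it ends at the same contact.

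**Which contact that is.** Section 8.10.3 has participants "return to the clinic 7 days after the last dose of study treatment for a follow-up visit and 28 days after the last dose"; the second of these is a telephone call. Section 4.1.1 puts the visit on Period 2 Day 13 and the call on Day 34. Section 5.3.2 also ties the follow-up visit to Day 13. The Schedule of Activities (Tables 1 and 2) puts the visit on Day 14 ± 1.

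**Adverse events.** Under Section 8.3.1, once treatment has begun, all events "will be reported until 28 days after the last dose of study treatment", whether or not they are thought related to it. Appendix 2, Section 3.2, lists "use of concomitant medications known to increase the occurrence of the event" among the points to weigh when judging causality.

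**The concern.** The causality guidance needs information that the recording rule does not require for most of the post-treatment window. The medicines that could be an alternative cause of a late event, such as something newly bought or prescribed after the visit, are the ones that fall outside the rule. Medicines given in response to an event are kept. The general restriction on medication ends at the same visit, so required recording stops just when other medicines become more likely.

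Incidence and severity of adverse events are secondary endpoints (Section 3, Table 3). The investigator's causality judgement also feeds expedited reporting (Appendix 2, Section 6). At stake is how well an event arising after the visit can be interpreted.

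**Working it through.** **Inputs**

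- Last dosing day: Period 2 Day 6, from Section 4.1.1 ("Treatment period: Days 1 to 6").
- Follow-up visit: 7 days after the last dose (Section 8.10.3); Day 13 (Section 4.1.1); Day 14 ± 1, that is Day 13 to Day 15 (Tables 1 and 2).
- Follow-up call: "28 days after the last dose of study treatment for a follow-up call" (Section 8.10.3); Day 34 (Section 4.1.1).
- Adverse event window: 28 days after the last dose (Section 8.3.1).

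**Reproducing the plan's own days**

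- Visit: 6 + 7 = Day 13. Call: 6 + 28 = Day 34. Both match Section 4.1.1.

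**Length of the gap**

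Days without required general recording = 28 − (visit day − 6). Share = that number / 28.

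| Visit day | Days covered | Days not covered | Share |
|---|---|---|---|
| 13 | 13 − 6 = 7 | 28 − 7 = 21 | 21/28 = 75.0% |
| 14 | 14 − 6 = 8 | 28 − 8 = 20 | 20/28 = 71.4% |
| 15 | 15 − 6 = 9 | 28 − 9 = 19 | 19/28 = 67.9% |

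Three quarters is exact for Sections 4.1.1 and 8.10.3. Across the Schedule's visit window the share is 68% to 75%.

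**After the change**

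With recording to Day 34, days not covered = 28 − (34 − 6) = 0 of 28.

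**Reading the Schedule of Activities**

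Table 1 has separate columns for the follow-up visit and the follow-up call. In the available text, the rows for adverse events and for previous and concomitant treatments each show one mark, in the same final position. Adverse events are plainly collected throughout, so that mark is probably what remains of a bar across the visits. If the adverse event bar reaches the call, the medication bar may reach it too. The layout is damaged and this cannot be confirmed.

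**Primary endpoints**

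The last scheduled pharmacokinetic sample is on Period 2 Day 7 (Table 2), before the follow-up visit. The gap cannot reach the primary comparison.

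**The case against.** The strongest reply is that the Schedule of Activities may already schedule medication collection at the call. Section 8.10.2 requires assessments to follow that Schedule, and Section 6.5.1 contains a sentence sending all concomitant medications to the eCRF without an end date. This stands as a real uncertainty. It does not remove the point: the only sentence that sets a recording window stops at the visit, and a Schedule that ran to the call would contradict it. The edit needed is the same either way.

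It can also be said that the term for the visit is used loosely. Section 5.3.2 refers to a final follow-up visit for tobacco, and Section 8.10.3 reports the visit and the call together as one completion visit in the eCRF. That is fair, but Section 8.10.3 also separates the two contacts by name and by day, and taking the term to mean the visit is the natural reading.

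Three stronger readings are tempting, and the documents do not support them.

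- *No medication data exist after the visit, so a causative drug would be missed.* Drugs given to manage an event are still recorded. Appendix 2, Section 3.2, asks the investigator to evaluate alternative causes, and Section 4 of that appendix obliges further evaluation of an event as medically indicated or requested. An investigator following these would probably ask about medication for a late event. What is missing is a requirement to record it systematically.
- *Attribution is biased between pitavastatin alone and the combination.* The interval after pitavastatin alone (at most 21 days, Section 4.1.1) does lie inside the recording window. But Table 6 groups events by treatment period without saying where follow-up events go, and the unequal observation comes mainly from the fixed sequence. Longer medication recording would not equalise it.
- *68% to 75% of the information is lost.* The figure is a share of calendar days. The documents do not say how many events are expected after the visit.

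**Conclusion.** The mismatch is real and minor. As written, general medication recording ends 19 to 21 days before adverse event collection does, which is 68% to 75% of the 28-day post-dose window.

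This rests on two assumptions: that the follow-up visit in Sections 1.1 and 6.5.1 is the clinic visit of Section 8.10.3, and that the Schedule of Activities does not override those sections. If the Schedule does extend to the call, the point becomes a contradiction between the Schedule and Section 6.5.1, which still has to be reconciled.

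The consequence is confined to interpreting late adverse events under a descriptive secondary safety objective in 18 healthy participants. There is no effect on the primary pharmacokinetic endpoints.

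**What to change.** - In Sections 1.1 and 6.5.1, move the end of medication recording from the follow-up visit to the follow-up call, 28 days after the last dose.
- State that the call collects concomitant medication together with adverse events.
- Check that the medication row in Table 1 of the Schedule of Activities covers the call, and correct it if it does not.
- In the same edit, reconcile the visit day between Sections 1.1, 4.1.1 and 5.3.2 (Day 13) and Tables 1 and 2 (Day 14 ± 1).

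The change concerns recording only and leaves the restriction period in Section 6.5.2 as it is. The cost is one added question on a call that already takes place, the matching eCRF entries and the protocol wording. The uncovered window falls from 19 to 21 days to none.

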### **6.5.2            Prohibited Therapy**

All medications (prescription and OTC) taken within 30 days of study screening will be recorded on the appropriate eCRF.

As a general rule, no concomitant medication will be permitted within 14 days prior to the first dosing or within 5 half-lives of the medication prior to the first dosing (whichever is longer), until the follow-up visit, with the exception of the cases listed in Permitted Therapy (See Section 6.5.1). Exceptions may be made on a case-by-case basis following discussion and agreement between the Investigator and the Sponsor after, the rationale for exception is discussed and clearly documented.

### **6.6                DOSAGE MODIFICATION**

No dose modification of RO7049389 or pitavastatin for safety reasons is expected in the study.

